5.13 Occurrence of Adverse Drug Reactions / Infections by Severity of Heart Failure

- (1) Patients to be tabulated and analyzed

Safety Analysis Set

- (2) Details of tabulation and analysis

Severity of heart failure will be classified into Class NYHA I, NYHA II, NYHA III, or NYHA IV or unknown for tabulation of type of adverse drug reactions, etc.

The method for tabulation of adverse drug reactions, etc. is same as that described in Section 5.1.

Total patients and patients who are taking concomitant insulin preparation, rapid-acting insulin secretagogues, SGLT-2 inhibitors, or other drugs will be tabulated.

- (3) Number of tables and figures

Table 5.13-1

5.14 Occurrence of Adverse Drug Reactions / Infections by Presence of Concurrent Stroke-related Disease

- (1) Patients to be tabulated and analyzed

Safety Analysis Set

- (2) Details of tabulation and analysis

Concurrent stroke-related disease will be classified into yes or no for tabulation of type of adverse drug reactions, etc.

The method for tabulation of adverse drug reactions, etc. is same as that described in Section 5.1.

Total patients and patients who are taking concomitant insulin preparation, rapid-acting insulin secretagogues, SGLT-2 inhibitors, or other drugs will be tabulated.

- (3) Number of tables and figures

Table 5.14-1

5.15 Occurrence of Adverse Drug Reactions / Infections by Mean Daily Dose of Nesina

- (1) Patients to be tabulated and analyzed

Safety Analysis Set

- (2) Details of tabulation and analysis

The mean daily dose of Nesina will be classified into > 25 mg, 25 to > 12.5 mg, 12.5 to > 6.25 mg, or 6.25 mg for tabulation of type of adverse drug reactions, etc.

The method for tabulation of adverse drug reactions, etc. is same as that described in Section 5.1.

Total patients will be tabulated.

- (3) Number of tables and figures

Table 5.15-1

5.16 Occurrence of Adverse Drug Reactions / Infections by Concomitant Medication (Diabetic Drug)

- (1) Patients to be tabulated and analyzed

Safety Analysis Set

- (2) Details of tabulation and analysis

Concomitant medications (diabetic drugs) will be classified into the following drugs: α -glucosidase inhibitors, thiazolidines, sulfonylureas, biguanides, rapid-acting insulin secretagogues, insulin preparations, DPP-4 inhibitors, GLP-1 receptor agonists, SGLT-2 inhibitors, combination of diabetic drugs, or other diabetic drugs, for tabulation of type of adverse drug reactions, etc.

The method for tabulation of adverse drug reactions, etc. is same as that described in Section 5.1.

Total patients and patients who are taking concomitant insulin preparation, rapid-acting insulin secretagogues, SGLT-2 inhibitors, or other drugs will be tabulated.

- (3) Number of tables and figures

Table 5.16-1

5.17 Occurrence of Adverse Drug Reactions / Infections by Presence of Concomitant Medication
(Protease Inhibitor)

- (1) Patients to be tabulated and analyzed

Safety Analysis Set

- (2) Details of tabulation and analysis

Concomitant medication (protease inhibitor) will be classified into yes, no, or unknown for tabulation of type of adverse drug reactions, etc.

The method for tabulation of adverse drug reactions, etc. is same as that described in Section 5.1.

Total patients and patients who are taking concomitant insulin preparation, rapid-acting insulin secretagogues, SGLT-2 inhibitors, or other drugs will be tabulated.

- (3) Number of tables and figures

Table 5.17-1

5.18 Occurrence of Adverse Drug Reactions / Infections by Presence of Concomitant Medication (Renal
Excretory Drug)

- (1) Patients to be tabulated and analyzed

Safety Analysis Set

(2) Details of tabulation and analysis

Concomitant medication (renal excretory drug) be classified into yes, no, or unknown for tabulation of type of adverse drug reactions, etc.

The method for tabulation of adverse drug reactions, etc. is same as that described in Section 5.1.

Total patients and patients who are taking concomitant insulin preparation, rapid-acting insulin secretagogues, SGLT-2 inhibitors, or other drugs will be tabulated.

(3) Number of tables and figures

Table 5.18-1

5.19 Change in Laboratory/Measured Data

5.19.1 Vital Signs

(1) Patients to be tabulated and analyzed

Safety Analysis Set

(2) Details of tabulation and analysis

In vital signs, summary statistics for pulse rate, blood pressure (systolic/diastolic), and weight will be calculated at each testing time point (start of Nesina treatment, 1 month, 3 months, 6 months, and 12 months after the start of Nesina treatment and last evaluation). For changes from the start of Nesina treatment, summary statistics and the mean 95% confidence intervals will be calculated.

Measured values (mean and standard deviation) will be plotted. For the changes, the mean changes will be created using a bar graph.

Total patients and patients who are taking concomitant insulin preparation, rapid-acting insulin secretagogues, SGLT-2 inhibitors, or other drugs will be tabulated.

(3) Number of tables and figures

Table 5.19.1-1 and Figures 5.19.1-1 to 5.19.1-4

5.19.2 Laboratory Values

(1) Patients to be tabulated and analyzed

Safety Analysis Set

(2) Details of tabulation and analysis

In laboratory values, summary statistics will be calculated for fasting triglyceride, total cholesterol, HDL-cholesterol, LDL-cholesterol, non-HDL cholesterol, serum creatinine, BUN, urinary albumin (corrected by creatinine), AST, ALT, γ -GTP, ALP, total bilirubin, amylase, lipase at each testing time point (start of Nesina treatment, 1 month, 3 months, 6 months, and 12 months after Nesina treatment and last evaluation). For changes from the start of Nesina treatment, summary statistics and the mean 95% confidence intervals will be calculated.

These laboratory values (mean and standard deviation) will be plotted. For the changes, the mean changes will be created using a bar graph.

Total patients and patients who are taking concomitant insulin preparation, rapid-acting insulin secretagogues, SGLT-2 inhibitors, or other drugs will be tabulated.

(3) Number of tables and figures

Table 5.19.2-1 and Figures 5.19.2-1 to 5.19.2-15

5.19.3 Electrocardiography

(1) Patients to be tabulated and analyzed

Safety Analysis Set

(2) Details of tabulation and analysis

For assessment of electrocardiogram, cross tabulation will be used for the categories described below.

Total patients and patients who are taking concomitant insulin preparation, rapid-acting insulin secretagogues, SGLT-2 inhibitors, or other drugs will be tabulated.

Parameter	Category
ECG results at start of Nesina treatment	Clinical abnormal findings (Yes or No) or Not performed
ECG results at 12 months after start of Nesina treatment	Clinical abnormal findings (Yes or No) or Not performed
ECG results at last evaluation	Clinical abnormal findings (Yes or No) or Not performed

(3) Number of tables and figures

Table 5.19.3

5.19.4 Waist Circumference

(1) Patients to be tabulated and analyzed

Safety Analysis Set

(2) Details of tabulation and analysis

For waist circumference, summary statistics will be calculated at each testing time point (at the start of Nesina treatment, 12 months after the start of Nesina treatment, and last evaluation). For changes from the start of Nesina treatment, summary statistics and the mean 95% confidence intervals will be calculated.

Measured values (mean and standard deviation) will be plotted. For the changes, the mean changes will be created using a bar graph.

Total patients and patients who are taking concomitant insulin preparation, rapid-acting insulin secretagogues, SGLT-2 inhibitors, or other drugs will be tabulated.

(3) Number of tables and figures

Table 5.19.4 and Figure 5.19.4

5.19.5 Tests for Coronary Atherosclerosis and Arteriosclerosis

(1) Patients to be tabulated and analyzed

Safety Analysis Set

(2) Details of tabulation and analysis

A listing of the following tests and the test results for coronary atherosclerosis and arteriosclerosis will be created: survey sheet number, treatment group, time point, test day, and details of tests (pulse wave velocity [PWV], cardio-ankle vascular index [CAVI], intima-media thickness [IMT], intra-vascular ultrasound [IVUS], and other [specify the details]).

(3) Number of tables and figures

Table 5.19.5

6.0 Efficacy Tabulation and Analysis

6.1 Changes in HbA1c

(1) Patients to be tabulated and analyzed

Efficacy Analysis Set

(2) Details of tabulation and analysis

For HbA1c (NGSP values), summary statistics will be calculated at each testing time point (start of Nesina treatment, 1 month, 3 months, 6 months, and 12 months after Nesina treatment and last evaluation). For changes, summary statistics and the mean 95% confidence intervals will be calculated and the paired t-test will be performed.

Measured values of HbA1c (NGSP values) will be plotted and for the changes a bar graph will be created excluding the unknown category.

Total patients and patients who are taking concomitant insulin preparation, rapid-acting insulin secretagogues, SGLT-2 inhibitors, or other drugs will be tabulated.

(3) Number of tables and figures

Table 6.1-1 and Figure 6.1-1

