## 3.0 Number of Planned Participants and the Rationales

### 3.1 Number of Planned Participants

1,000 participants

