### 3.2 Rationales

The Specified Drug-use Survey of Nesina has been conducted in type 2 diabetes mellitus patients who have had an inadequate response to diet/exercise therapies only or diet/exercise therapies plus  $\alpha$ -glucosidase inhibitors, thiazolidines, sulfonylureas, or biguanides. In the future, the specified drug-use survey of complication with Nesina and insulin preparations and insulin

secretagogues is also expected to be conducted.

Therefore, the planned participants was established as 1,000 to collect as many as participants who receive a long-term complication therapy with Nesina and these hypoglycemic agents (e.g., insulin preparations, rapid-acting insulin secretagogues).

In the pooled tabulation of participants in the past Nesina Specified Drug-use Survey (as of November 30, 2013; Safety Analysis Set, 10,025 participants), the proportion of participants was as follows: elderly, 58.0%; renal impairment participants, 15.1%; and hepatic impairment participants, 13.3%. By establishment of the planned participants of 1,000 in this survey, data will be collected from approximately 600 elderly participants, approximately 150 renal impairment participants, and approximately 100 hepatic impairment participants. This establishment is not based on the statistical evidence.

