##### 4.1 Inclusion Criteria

Patients who meet the following criterion are included in this survey:

Patients who have had an inadequate response to the following medications/therapies:

- Use of one hypoglycemic agent such as insulin preparations and rapid-acting insulin secretagogues, excluding other types of hypoglycemic agents (e.g.,  $\alpha$ -glucosidase inhibitors, thiazolidines, sulfonylureas, biguanides)\*, in addition to dietary/exercise therapy

\*For use of Nesina Tablets in combination with these agents, a specified drug-use survey is currently ongoing.

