9.2.3 Details of Treatment

1) Matters to be surveyed

Details of Nesina treatment (daily dose, administration period, and reason for discontinuation), and status of concomitant medications (hypoglycemic agents\*) (yes/no, drug name, daily dose, route of administration, administration period, and objective of administration)

\*Hypoglycemic agents which are discontinued within 3 months prior to Nesina treatment are included.

2) Survey period

Period from the start of Nesina treatment to 12 months after treatment (or treatment discontinuation)

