Mean daily dose of Nesina	
Calculate using the following formula: Total of “daily dose of Nesina \square Nesina treatment period at the relevant dose” / Nesina treatment period. For the calculation of Nesina treatment period, refer to the above.
 
If the daily dose of Nesina is a number outside specification in the survey sheet , handle the dose as follows:
 
 • < 6.25 mg \rightarrow 3.125 mg • > 25 mg \rightarrow 50 mg
HbA1c (NGSP value)	
The NGSP value only will be used in this analysis.
 
For the HbA1c (JDS value), calculate using the following formula: NGSP value (%) = $1.02 \times \text{JDS value (\%)} + 0.25\%$
 
The HbA1c (international standard value) will be handled as the NGSP value.

Change in HbA1c	For HbA1c converted to the NGSP value, calculate using the following formula: Laboratory value at each testing time point – Laboratory value at the start of Nesina treatment.
Glycemic control achievement rate	
Divide the following two categories for the glycemic control achievement rate: HbA1c (NGSP converted value) [Unit %] NGSP (%): < 6.0, \geq 6.0 / < 7.0, \geq 7.0

non-HDL cholesterol	Calculate using the following formula: “Total cholesterol” – “HDL cholesterol.”
HOMA-R	Calculate using the following formula: Fasting insulin level ($\mu\text{U/mL}$) \times Fasting blood glucose level (mg/dL) / 405. Indicate to one decimal place rounded from two decimals. For calculation, use the values of fasting insulin level and fasting blood glucose level measured at the same day.
HOMA- β	
Calculate using the following formula: Fasting insulin level ($\mu\text{U/mL}$) \times 360 / (Fasting blood glucose level [mg/dL] – 63). Indicate to one decimal place rounded from two decimals.
 
For calculation, use the fasting insulin level and fasting blood glucose level measured at the same day. Do not use the fasting blood glucose level of < 63 for calculation

Summary statistics	Number of patients, mean, standard deviation, minimum, first quartile, median, third quartile, and maximum.

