1.4 Level of Significance and Confidence Coefficient

Two-sided 5%, two-sided 95%.

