4.0 Details of Treatment

(1) Patients to be tabulated and analyzed

Safety Analysis Set

(2) Details of tabulation and analysis

Each parameter will be classified by the categories described below to tabulate the number of patients and frequency.

Total patients and patients who are taking concomitant insulin preparation, rapid-acting insulin secretagogues, SGLT-2 inhibitors, or other drugs will be tabulated.

Parameter	Category
Initial dose of Nesina	25 mg, 12.5 mg, 6.25 mg, or other
Mean daily dose of Nesina	> 25 mg, 25 to >12.5 mg, 12.5 to > 6.25 mg, or ≤ 6.25 mg
Nesina treatment period	Summary statistics
	1 to 60 days, 61 to 136 days, 137 to 273 days, 274 to 455 days, ≥ 456 days
Administration of prior medication (diabetic drug)	No, Yes, or Unknown
Prior medications (diabetic drugs)	
α-glucosidase inhibitors, thiazolidines, sulfonylureas, biguanides, rapid-acting insulin secretagogues, insulin preparations, DPP-4 inhibitors, GLP-1 receptor agonists, SGLT-2 inhibitors, combination of diabetic drugs, or other diabetic drugs
 
For the proportion, the number of patients with “Yes” for administration of prior medication (diabetic drug) will be denominator.

Administration of prior medication (other than diabetic drug)	No, Yes, or Unknown
Administration of concomitant medication (diabetic drug)	No, Yes, or Unknown
Concomitant medications (diabetic drugs) (overlapped)	
α-glucosidase inhibitors, thiazolidines, sulfonylureas, biguanides, rapid-acting insulin secretagogues, insulin preparations, DPP-4 inhibitors, GLP-1 receptor agonists, SGLT-2 inhibitors, combination of diabetic drugs, or other diabetic drugs
 
For the proportion, the number of patients with “Yes” for administration of concomitant medication (diabetic drug) will be

Parameter	Category
	denominator.
Administration of concomitant medication (hypertension drug)	No, Yes, or Unknown
Concomitant medications (hypertension drugs) (overlapped)	ARB, Ca antagonists, ACE inhibitors, diuretics, α blockers, $\alpha\beta/\beta$ blockers, complication of hypertension drugs, or other For the proportion, the number of patients with “Yes” for administration of concomitant medication (hypertension drug) will be denominator.
Administration of concomitant medication (dyslipidaemia drug)	No, Yes, or Unknown

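### The uncontrolled HbA1c change in SAP 6.1–6.2 mixes Nesina with recent starts, dose changes and later intensification of background diabetic drugs, because no rule requires or identifies stable background therapy

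*SAP*

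**What the plan says.** The survey's aim (Protocol 2.0) is the safety and efficacy of Nesina in patients inadequately controlled on a background agent. Eligibility covers "Patients who have had an inadequate response to the following medications/therapies" (Protocol 4.1), followed by use of one agent such as insulin or a rapid-acting secretagogue. No minimum time on that agent, stable dose or run-in is stated.

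SAP 1.1 defines the HbA1c change as "Laboratory value at each testing time point – Laboratory value at the start of Nesina treatment". SAP 6.1 adds: "For changes, summary statistics and the mean 95% confidence intervals will be calculated and the paired t-test will be performed". SAP 6.2 tabulates the achievement rate at the same time points. Testing is two-sided at 5% (SAP 1.4), and there is no control group.

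Four other rules bear on background drugs.

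- **Treatment groups (SAP 1.1).** Each single-class column requires use of that class both within the 3 months before Nesina and during Nesina, and no use of the other two named classes.
- **Efficacy exclusion (SAP 2.0).** The only exclusion specific to efficacy is use of none of the three classes.
- **Cut-off of values (SAP 1.5).** For patients not on Nesina at 12 months, values count up to the end of Nesina treatment. For the others, all values count.
- **Stratification (SAP 6.4 viii).** Results are split by concomitant diabetic drug class. SAP 1.1 defines concomitant as taken after the Nesina start date.

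Drug name, daily dose and administration period are collected, and "Hypoglycemic agents which are discontinued within 3 months prior to Nesina treatment are included" (Protocol 9.2.3).

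**The concern.** Without a comparator, a fall in HbA1c after the start of Nesina is the sum of everything that changed from then on. If the background agent was begun or raised shortly before Nesina, or another drug was added later, its effect falls inside the same paired difference. If background therapy was reduced or stopped, the difference is pulled the other way. The plan neither keeps these patients apart nor counts them at each time point, so a reader of the 12-month figure cannot tell how much of it comes from patients whose other treatment was unchanged. The interval and p-value do not help, because they describe sampling error around the mixed quantity.

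**Working it through.** **No plan figure to reproduce.** The planned size is "1,000 participants" (Protocol 3.1), and Protocol 3.2 says of it: "This establishment is not based on the statistical evidence". No effect size, SD, power or dropout rate is given. The check is therefore a trace of the rules, followed by a labelled illustration.

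**Step 1: trace three situations through the SAP.**

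- *Qualifying agent begun two weeks before Nesina, response already judged inadequate.* Protocol 4.1 sets no minimum duration, and the group rule is met because the class was used before and during Nesina. The baseline window in SAP 1.5 runs from day −30 to day 0. If the only baseline HbA1c is from day −25, it predates the agent, and the agent's whole effect enters the change. With a day 0 baseline, whatever effect comes later still enters.
- *Insulin dose raised at month 4.* The patient stays in the insulin column. No value is removed or flagged.
- *Sulfonylurea or biguanide added at month 9.* The group rule excludes only the other two named classes, so the patient stays in the column. In 6.4 viii this drug shares a stratum with the same class taken since the start, because any use after the start counts as concomitant. If the added drug is one of the other two named classes, the patient leaves the single-class columns, but the SAP 2.0 table does not remove the patient from the Efficacy Analysis Set.

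**Step 2: size, on assumptions.** Let f be the share of patients with a background change and d its effect on HbA1c in points. The shift in the mean is f × d.

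- Low end: 0.10 × (−0.5) = −0.05
- High end: 0.30 × (−1.5) = −0.45

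The 95% half-width is 1.96 × SD / √n.

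- n = 900, SD 1.2: 1.96 × 1.2 / 30 = 0.078
- n = 1,000: 0.050, 0.062 and 0.074 for SD 0.8, 1.0 and 1.2

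**Step 3: effect on the paired test if Nesina had no effect.** By the normal approximation, P(reject) = Φ(|f × d|/SE − 1.96) + Φ(−|f × d|/SE − 1.96), with SE = SD/√n. At n = 1,000 and SD 1.0, SE = 0.0316.

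- f = 0.10, d = −0.5 (shift −0.05): 0.353, with a range of 0.261 to 0.507 over SD 1.2 to 0.8
- f = 0.20, d = −0.5 (shift −0.10): 0.885, with a range of 0.750 to 0.977
- The same −0.10 shift at SD 1.0: 0.609 with n = 500 and 0.293 with n = 200

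The shift f × d does not depend on n. A larger survey only makes it more likely to reach significance. With d positive, the shift has the same size and the opposite sign.

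f, d, SD and the 900 analysed patients are all assumptions.

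**The case against.** The strongest reply is that the plan does not ignore background therapy. The SAP 1.1 group rule brings pre-start exposure into every efficacy column, and a patient who takes a second named class drops out of the single-class columns. Protocol 4.1 also requires that the response has already been judged inadequate, which is a condition even without a number of weeks. This stands as far as it goes, but it is a rule about use, not about duration or dose.

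A reader might infer that insulin begun on the same day as Nesina could enter. The documents do not support that: it conflicts with having already had an inadequate response and with the requirement of use before Nesina. A reader might also infer that switches from another DPP-4 inhibitor make up a sizeable share, because SAP 4.0 lists that class among prior drugs. That list is generic. A patient on insulin plus a DPP-4 inhibitor fits poorly with the one-agent condition in Protocol 4.1, and a patient using none of the three classes is excluded from efficacy by SAP 2.0. No share can be put on such switches.

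The reply can add that the SAP makes no causal statement. This is a survey of routine practice that tabulates changes, with no confirmatory hypothesis. That is correct, and it explains why no run-in was imposed. It does not explain why the recorded doses and dates go unused, and a paired test under an efficacy heading invites the causal reading.

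Finally, every input to the size is assumed, and −0.45 multiplies two unfavourable values. That also stands.

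**Conclusion.** The point holds as a limit on interpretation that the sponsor can reduce at low cost. The reported HbA1c change and achievement rate mix Nesina with recent starts or dose changes of the qualifying agent and with later intensification, and no planned table separates them.

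The size and direction cannot be determined from the documents. The range of −0.05 to −0.45 points is an illustration that rests on 10–30% of patients being affected by −0.5 to −1.5 points each. It shows only that a modest share could exceed a half-width of about 0.08. It is not an estimate for this survey. A reader should not infer that the result is known to overstate Nesina's effect, since reductions in background therapy act the other way. Nor does the SAP state that the change is caused by Nesina.

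**What to change.** In SAP 6.1 and 6.2, for the total and each treatment group:

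1. Add HbA1c change and achievement rate in patients with no diabetic drug started, stopped or dose-changed in the 3 months up to the Nesina start, as far as the collected data show. Show patients with imputed dates or unknown doses separately and do not count them as stable. This matters because SAP 1.1 sets a start date with unknown month and day to January 1, so a drug begun in November can look ten months old. The subset uses only information up to the start, so it does not select on response.
2. At each time point, tabulate the number of patients with a diabetic drug added or dose-increased since the start. Add a supportive analysis that excludes HbA1c values after the first added drug class, and state that this selects on response. Do not carry values forward: that would freeze HbA1c at the point where treatment was changed, and would give a change of zero if the addition came before the first follow-up value. Using an added class as the trigger, and not any dose increase, keeps routine insulin titration from emptying the insulin column.
3. Keep the all-patient result and describe it as change during Nesina treatment, not as Nesina's add-on effect.

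The cost is SAP wording and two table blocks. Drug, dose and period are already collected (Protocol 9.2.3), although the stated survey period begins at the Nesina start, so earlier dose changes of a continuing drug may be incompletely recorded. The stable subset will be smaller and its interval wider.

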## 6.0 Number of Scheduled Sites by Department

Internal medicine or other department: Approximately 200 sites

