2.0 Disposition of Patients (Patient Diagram)

(1) Patients to be tabulated and analyzed

Registered patients

(2) Details of tabulation and analysis

The following will be tabulated: the number of registered patients, number of medical site at which patients is registered, number of patients whose survey sheets are collected, number of patients whose survey sheets are not collected, number of patients in the Safety Analysis Set, number of patients in the Not Safety Analysis Set, number of patients in the Efficacy Analysis Set, and number of patients in the Not Efficacy Analysis Set.

For the number of medical sites at which patients are registered, do not duplicate the same medical site with different departments.

For patients whose survey sheets are not collected, tabulate the number of patients for each reason for not collected survey sheets.

For the Not Safety Analysis Set and Not Efficacy Analysis Set, the number of patients will be tabulated for each reason for exclusion to create the list.

The following is the handling of the decision whether patients who meet the following criteria should be evaluated:

Criterion	Safety evaluation	Efficacy evaluation
Pre-agreement administration [found after administration]	×	×
Registration 15 days after prescription of Nesina [found after registration]	×	×
Nesina taking not confirmed [after the end of patient registration period]	×	×
No data for post-administration of Nesina	×	×
Not using any of the 3 combination drugs (the treatment group will be classified as "Other.") (1) With insulin preparation (2) With rapid-acting insulin secretagogues (3) With SGLT-2 inhibitors	○	×

○ Included, × Excluded or not evaluated

(3) Number of tables and figures

Figure 2.0-1 and Table 2.0-1

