5.4 Patient Demographics and Frequency of Adverse Drug Reactions / Infections by Treatment

5.4.1 Patients demographics and Frequency of Adverse Drug Reactions / Infections by Treatment

(1) Patients to be tabulated and analyzed

Safety Analysis Set

(2) Details of tabulation and analysis

Each parameter will be categorized by the categories described below to tabulate the percent of patients with adverse drug reactions, etc.

The Fischer exact test will be used for parameters without rank data. The Mann-Whitney U test will be used for parameters with rank data. (The tests will be used for parameters with asterisk [*].)

Total patients and patients who are taking concomitant insulin preparation, rapid-acting insulin secretagogues, SGLT-2 inhibitors, or other drugs will be tabulated.

Parameter	Category
Sex*	Male, Female
Age*	< 65 years, ≥ 65 years
	< 75 years, ≥ 75 years
Concurrent liver disorder*	No, Yes
Severity of hepatic	Normal, Grades 1, 2, and 3, or Unknown

Parameter	Category
impairment*	
Concurrent renal disorder*	No, Yes
Severity of renal impairment* (eGFR)	Normal + Mild, Moderate + Severe, or Unknown
Severity of renal impairment* (serum creatinine)	Normal + Mild, Moderate + Severe, or Unknown
Concurrent heart disease*	No, Yes
Details of concurrent heart disease (overlapped)	Cardiac failure, myocardial infarction, or angina pectoris
Concurrent cardiac failure*	No, Yes
Severity classification of cardiac failure (NYHA classification)*	Classes NYHA I, NYHA II, NYHA III, and NYHA IV, or Unknown
Concurrent stroke-related disease*	No, Yes, or Unknown
Mean daily dose of Nesina	> 25 mg, 25 to >12.5 mg, 12.5 to > 6.25 mg, or ≤ 6.25 mg
Administration of concomitant medication (diabetic drug)	No, Yes
Concomitant medications (diabetic drugs) (overlapped)	α-glucosidase inhibitors, thiazolidines, sulfonylureas, biguanides, rapid-acting insulin secretagogues, or insulin preparations, DPP-4 inhibitors, GLP-1 receptor agonists, SGLT-2 inhibitors, combination of diabetic drugs, or other diabetic drugs
Administration of concomitant medication (protease drug)*	No, Yes, or Unknown
Administration of	No, Yes, or Unknown

Parameter	Category
concomitant medication (combined with renal excretory drug)*	

(3) Number of tables and figures

Table 5.4.1-1

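### The 95% intervals and paired t-tests for mean change treat patients as independent although they are enrolled at about 200 sites, so they are too narrow if changes correlate within site

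*SAP*

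**What the plan says.** SAP 1.4 sets one standard for all inference: a two-sided 5% level and 95% confidence. It is applied to mean changes in two groups of sections.

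- **Intervals and tests.** Section 6.1 (HbA1c) says: "For changes, summary statistics and the mean 95% confidence intervals will be calculated and the paired t-test will be performed". Section 6.3 does the same for fasting glucose, insulin, glucagon, HOMA-R and HOMA-β. Section 6.4 repeats it for HbA1c change across eight factors.
- **Intervals only.** Section 5.19.2 (laboratory values) says: "For changes from the start of Nesina treatment, summary statistics and the mean 95% confidence intervals will be calculated". Sections 5.19.1 (vital signs) and 5.19.4 (waist circumference) follow the same pattern.

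The patients are nested in sites. Protocol 3.1 plans "1,000 participants", and Protocol 6.0 reads "Internal medicine or other department: Approximately 200 sites". In the SAP, site appears only as a count in the disposition table (2.0), with this rule: "For the number of medical sites at which patients are registered, do not duplicate the same medical site with different departments". Neither document has a site term, mixed model, robust standard error or site sensitivity analysis.

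**The concern.** An ordinary t interval for a mean assumes that each patient contributes independent information. When patients at a site tend to change together, the true variance of the mean exceeds the one the formula uses. The interval is then too short and the paired t-test rejects too often.

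The documents make some within-site correlation of change plausible, without proving it. The survey runs in routine practice (Protocol 2.0). Concomitant hypoglycaemic drugs are recorded, not assigned (Protocol 9.2.3). Diet and exercise compliance is graded against what the patient was told to do (Protocol 9.2.4). HbA1c may arrive on more than one scale (SAP 1.1).

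Uneven site sizes are plausible too. Patients are enrolled as they are prescribed the drug (Protocol 7.3), enrolment closes once the overall total is reached (Protocol 8.0), and the available text gives no cap per site.

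What is at stake is whether the stated 95% and 5% are what the tables deliver. The intervals and tests recur across time points, treatment groups and the 6.4 factors, so some borderline results are likely to be read at face value.

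**Working it through.** The plan has no figure to reproduce. Of the sample size, Protocol 3.2 says "This establishment is not based on the statistical evidence", and no SD, power, precision or design effect is given.

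**Inputs**
- n = 1,000 planned patients (Protocol 3.1); k ≈ 200 sites (Protocol 6.0); mean site size m = 1,000/200 = 5.
- z = 1.96 (from SAP 1.4).
- ICC of the change: not in the documents; assumed 0, 0.02, 0.05 and 0.10.
- CV of site size: not in the documents; assumed 0 (equal sites) or 1 (very uneven).

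**Formulas**
- Design effect: DE = 1 + (m(1 + CV²) − 1) × ICC. The multiplier of ICC is 5 − 1 = 4 for equal sites and 5 × 2 − 1 = 9 for CV 1.
- Correct width relative to planned width: √DE.
- Real two-sided error of a nominal 5% test: 2(1 − Φ(1.96/√DE)).

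| ICC | DE, equal sites | Width | Real error | DE, CV 1 | Width | Real error |
|---|---|---|---|---|---|---|
| 0 | 1.00 | ×1.00 | 5.0% | 1.00 | ×1.00 | 5.0% |
| 0.02 | 1 + 4 × 0.02 = 1.08 | ×1.04 | 5.9% | 1 + 9 × 0.02 = 1.18 | ×1.09 | 7.1% |
| 0.05 | 1 + 4 × 0.05 = 1.20 | ×1.10 | 7.4% | 1 + 9 × 0.05 = 1.45 | ×1.20 | 10.4% |
| 0.10 | 1 + 4 × 0.10 = 1.40 | ×1.18 | 9.8% | 1 + 9 × 0.10 = 1.90 | ×1.38 | 15.5% |

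**Simulation check** (one-sample t-test on changes, 200 sites, 1,000 patients, 4,000 replicates). With equal sites, coverage of the nominal 95% interval was 94.9%, 93.6% and 90.5% at ICC 0, 0.05 and 0.10; the formula gives 95.0%, 92.6% and 90.2%. With uneven sites it was 94.9%, 89.8% and 82.4%, against 95.0%, 89.6% and 84.5%. The simulated sizes are slightly more uneven than CV 1 (CV² about 1 + 1/5 = 1.2). At ICC 0.10 that implies DE = 1 + (5 × 2.2 − 1) × 0.10 = 2.0 and coverage of about 83.4%.

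**On the HbA1c scale.** With an assumed SD of change of 1.0 percentage point and all 1,000 patients, the half-width is 1.96 × 1.0/√1,000 = 0.062. With equal sites it becomes 0.062 × √1.20 = 0.068 at ICC 0.05 and 0.062 × √1.40 = 0.073 at ICC 0.10. For an assumed SD of 0.8 the three values are 0.050, 0.054 and 0.059; for 1.2 they are 0.074, 0.081 and 0.088.

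**Treatment groups.** Take an assumed group of 300.
- Spread over all 200 sites, m = 1.5. DE = 1 + 0.5 × ICC = 1.01, 1.025 and 1.05 at ICC 0.02, 0.05 and 0.10, so widths grow by only 0.5% to 2.5%.
- Concentrated at 30 sites (also assumed), m = 10. At ICC 0.05, DE = 1 + 9 × 0.05 = 1.45 and the width grows by 20%.

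**The case against.** The strongest reply is that little depends on this. The survey is single-arm and descriptive, no decision rule rests on a p-value, and the sample size has no statistical basis. Change scores cancel stable differences in level between sites, so only the ICC of change matters, and nobody has stated it. The 1,000 is planned enrolment: patients on none of the three combination drugs leave the Efficacy Analysis Set (SAP 2.0), and each time point uses only the values available. With 200 contributing sites, m for HbA1c change is therefore below 5. No passage says that patients at a site share a laboratory or a single physician.

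Most of this stands and limits the size of the point. It does not remove it. The SAP chose to print intervals and p-values at a stated level, and gives the reader nothing with which to judge how far that level is off.

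A reader might infer more than the documents support:

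- **That the intervals are shown to be too narrow.** They are too narrow only if the ICC of change is positive. The 38% and 15.5% need the highest assumed ICC together with CV 1.
- **That the Fisher and Mann-Whitney tests in SAP 5.4.1 are too liberal as well.** For factors that vary within a site, such as sex or age, ignoring site can make a test conservative. The direction is unknown. Causality grading by the investigator bears on these reaction counts, not on intervals for mean change.
- **That small treatment groups suffer most.** The formula says the opposite unless a group is concentrated at few sites.
- **That the inflated test error covers laboratory changes.** Section 5.19 plans no tests. Sections 5.19.3, 5.19.5 and 6.2 contain no inference at all.

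**Conclusion.** The point holds as a conditional one, limited to mean changes in SAP 5.19.1, 5.19.2, 5.19.4, 6.1, 6.3 and 6.4. The planned method ignores site, and any positive within-site correlation of change makes these intervals too narrow; in 6.1, 6.3 and 6.4 it also makes the paired t-tests too liberal. For the whole planned sample the effect is small to moderate over ICC 0.02 to 0.10 with equal sites, and reaches the upper figures in the table only if site sizes are also very uneven. The overall HbA1c conclusion is unlikely to turn on it; borderline results could. The size rests on assumed ICC and CV values and on m = 5, which is an upper value for the Efficacy Analysis Set if all 200 sites contribute. This is a cheap improvement, not a flaw that invalidates the plan.

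**What to change.** In SAP 5.19.1, 5.19.2, 5.19.4, 6.1, 6.3 and 6.4, compute the 95% interval for mean change with cluster-robust (sandwich) standard errors by site. In 6.1, 6.3 and 6.4, base the test of mean change on the same standard error. Define site as SAP 2.0 already does, with departments of one institution counted together. The site name is on the enrolment sheet (Protocol 9.1).

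Report the distribution of patients per site and the observed ICC of change, so that readers can see how much the adjustment matters.

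Where a subgroup comes from few sites, use a small-sample correction, or keep the ordinary interval and say so. With about 200 sites overall, the robust standard errors are reliable for the full sets.

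Keep the Fisher and Mann-Whitney tests in 5.4.1. Replacing them with clustered models for sparse reactions is a debatable trade when the direction of error is unknown.

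The cost is a few lines of SAP text, a little programming and slightly wider intervals. No new data are needed, and if the ICC is 0 the results are essentially unchanged.
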